5.3 Eligibility Criteria

Assessment for eligibility criteria is based on medical records of the site and interview with a candidate patient. Subjects must meet ALL of the inclusion criteria to be considered for the clinical investigation. If ANY of the exclusion criteria are met, the subject is excluded from the clinical investigation and cannot be registered. If any clinical and/or laboratory tests are required for patient screening and are not included in a site's standard tests, they must be completed after written informed consent is obtained.

5.3.1 Inclusion Criteria

- 1. Age ≥18 years
- 2. Subject is planned to have an ablation procedure that requires multiple sheaths insertion in a single femoral vein
- 3. All the access sites are planned to be treated with Perclose SMC
- 4. Written informed consent is obtained prior to the procedure

5.3.2 Exclusion Criteria

Site standard exclusion criteria should be used for eligibility of ablation procedure. In addition, the exclusion criteria for Perclose SMC procedure listed below will be applied.

- 1. Visible vascular thrombus (angiographic or ultrasound) in the ipsilateral leg prior to the ablation procedure
- 2. Prior ipsilateral deep vein thrombosis within 6 months
- 3. International Normalized Ratio >3.5 for patients on warfarin
- 4. Subject who is not able to ambulate pre-procedure
- 5. Women who are pregnant (based on site standard pre-procedure pregnancy test)
- 6. Has active symptoms and/or a positive test result of COVID-19 or other rapidly spreading infectious agent within the prior 2 months

5.4 Subject Registration

Registration is defined as the time at which, the Perclose SMC is inserted into the body. This study allows either pre-close or post-close technique. If pre-close technique is used, the subject is considered to be registered even before the ablation procedure.

5.4.1 Enrollment of Medicare Beneficiaries

This clinical investigation will enroll Medicare beneficiaries and therefore conforms to all standards of Medicare coverage requirements. The Risks and Benefits section describes how all enrolled subjects, including Medicare beneficiaries, may be affected by the device under investigation.

A portion of the subjects enrolled in the clinical investigation display characteristics consistent with the Medicare population based on age. The clinical investigation results will be analyzed by age (< 65 years and > 65 years) and compared to ensure that the outcomes are similar between the Medicare and non-Medicare populations.

5.4.2 Historically Under-Represented Demographic Subgroups

The Sponsor intends to implement FDA's guidance on sex-specific data in medical device clinical investigations to ensure adequate representation of women and other traditionally underrepresented demographic subgroups in this clinical investigation. As noted in the guidance, some barriers to participation of women and ethnic minorities in clinical investigations have traditionally been:

- Lack of understanding about main obstacles to participation of such subgroups in clinical research
- Inclusion/exclusion criteria potentially not needed to define the clinical investigation population may unintentionally exclude specific subgroups
- Under diagnosis of disease etiologies and pathophysiology leading to under referral of demographic subgroups
- Avoidance of specific subgroups by investigators and Sponsors due to the perception that it takes more time and resources to recruit them
- Fear of fetal consequences (for female participants)
- Family responsibilities limiting women's ability to commit time for follow-up requirements

5.5 Subject Withdrawal and Discontinuation

Each registered subject shall remain in the clinical investigation until completion of the 30-day follow-up period; however, a subject's participation in any clinical study is voluntary and the subject has the right to withdraw at any time without penalty or loss of benefit.

however, a subject's participation in any clinical investigation is voluntary and the subject has the right to withdraw at any time without penalty or loss of benefit. Conceivable reasons for discontinuation may include, but not be limited to, the following:

- Subject death
- Subject voluntary withdrawal
- Subject lost-to follow-up as described below

• Subject's follow-up is terminated according to Section 3.3, Suspension or Early Termination of the Clinical Investigation.

Sites must notify the Sponsor of the reason(s) for subject discontinuation. Investigators must also report this to their respective IRB as defined by their institution's procedure(s).

No additional follow-up is required or data recorded from subjects once withdrawn from the clinical investigation, except for the status (deceased/alive).

However, if a subject withdraws from the investigation due to problems related to the safety or performance of the device under investigation, the investigator shall ask for the subject's permission to follow his/her status/condition outside of the clinical investigation.

In case of subject withdrawal of consent, the site should make attempts to schedule the subject for a final clinical investigation visit. At this final follow-up visit, the subject will undergo the following assessments:

- Review and report adverse events in electronic case report form (eCRF)
- · Review and report protocol and concomitant medications in eCRF
- Complete subject reported outcomes in eCRF

Lost-to-Follow-up

If the subject misses two consecutive scheduled follow-up time points and the attempts at contacting the subject detailed below are unsuccessful, then the subject is considered lost-to-follow-up. Site personnel shall make all reasonable efforts to locate and communicate with the subject (and document these efforts in the source documents), including the following, at each contact time point:

- A minimum of two telephone calls on different days over the specified follow-up windows to contact the subject should be recorded in the source documentation, including date, time and initials of site personnel trying to make contact.
- If these attempts are unsuccessful, the site should send a letter (certified if applicable) to the subject.
- If a subject misses one or more non-consecutive follow-up contact time points, it will be considered a missed visit. The subject may then return for subsequent visits. If the subject misses two consecutive time points and the above-mentioned attempts at communicating with the subject are unsuccessful, the subject will be considered lost-to-follow-up.

Note: Telephone contact with General Practitioner, non-clinical investigation cardiologist or relative without the presence of the subject or indirect documentation obtained via discharge letters will not be considered as subject contact.

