5.7 Total Expected Duration of the Clinical Study

The expected duration of registration is 3 months. The expected duration of each subject's participation is 1 month, including the scheduled visits and data collection for this clinical study. Subjects will exit the trial at the end of their 1-month follow-up visit. Therefore, the total duration of the clinical investigation is expected to last 4 months, consisting of approximately 3 months of registration plus 1 month of follow-up.

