 - Requiring surgical or percutaneous repair (major)
 - Not requiring surgical or percutaneous repair
- Infection
 - requiring oral, intramuscular, or intravenous antibiotics, or leading to a prolonged hospitalization (major)
 - Not requirng above (minor)
- No flow-limiting suture material
- Access site-related nerve injury
 - Persisting for > 30 days
 - Resolved \leq 30 days
- Pulmonary embolism
 - Requiring surgical or endovascular intervention and/or resulting in death, to be confirmed by CT pulmonary angiography, lung ventilation/perfusion scan (VQ scan), or autopsy
 - Not requiring or resulting above
- Other

6.5 30-day Follow-up Assessments

All subjects registered in the study must have follow-up assessments at 30 days (+/- 7 days).

If a subject has any access site-related vascular complications (either symptomatic/visible or asymptomatic/nonvisible), nerve injury, or infection at discharge, the follow-up must be done by a site visit. For those subjects who had vascular complications detected on femoral DUS at discharge, a repeat femoral DUS must be done at the 30-day visit in the leg or legs in which the vascular complication(s) was (were) found at discharge.

For a subject who does not have an access site-related vascular complication, nerve injury, or infection, 30-day follow-up can be done by telephone contact. The investigator or the designee should ask whether the subject has any signals of vascular complications. If the subject has a

susceptive signal, he/she is asked to visit the hospital for further assessment, and this site visit is regarded as the 30-day follow-up. If the telephone contact is done within the time window, it is not regarded as the deviation even though the site visit occurs outside of the window.

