6.7 Scheduled Event

CIP Activity	Baseline (within 30 days prior to index procedure)	Pre-Procedure	Procedure	Discharge	30 days (± 7 days) office visit	Unscheduled visits
Subject Medical/Clinical History (Age, Sex, Risk Factors)	✓					
Subject Informed Consent	~					
Inclusion/Exclusion Criteria	~					
Duplex Ultrasound ¹				✓	√1	√2
Concomitant Medications	✓	~		✓	✓	√2
Procedure Medications			✓			
Procedure Information			~			
Perclose Usage Information			✓			
Heparin Reversal			✓			
Adverse Events			✓	✓	✓	√2

¹ 30-day DUS is only required if a complication is observed at discharge DUS. The core laboratory will review the DUS images and provide its assessment to investigators to determine whether 30-day DUS is required.

² Unscheduled visits are to occur per site standard of care. Data to be collected if performed. Protocol deviations will not be required if not done.

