8.4 Timing of Analysis

The primary analysis will be performed after database lock when all subjects have completed their 30-day follow-up visit.

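### The lost-to-follow-up definition needs two consecutive missed time points, but the schedule has one after discharge, so disposition would show zero lost whatever happens

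*Combined protocol and SAP*

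**What the plan says.** Section 5.5 of the protocol lists loss to follow-up among the reasons for discontinuation and defines it in the paragraphs below the list. The definition has two parts: the subject must miss enough visits, and the contact attempts must fail. The first part reads "If the subject misses two consecutive scheduled follow-up time points", and the closing bullet repeats it: "If the subject misses two consecutive time points". The attempts are at least two telephone calls on different days over the follow-up window, then a letter, and they are required at each contact time point. For anything less, Section 5.5 says: "If a subject misses one or more non-consecutive follow-up contact time points, it will be considered a missed visit". Such a subject may come back for later visits.

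The schedule is short. Section 6.5 says: "All subjects registered in the study must have follow-up assessments at 30 days (+/- 7 days". The follow-up is a site visit for subjects with a complication at discharge and may be a telephone contact for the others. In the Section 6.7 table the only scheduled column after discharge is "30 days (± 7 days) office visit"; the one remaining column is for unscheduled visits. Section 5.7 closes participation there: "Subjects will exit the trial at the end of their 1-month follow-up visit". Section 8.4 places the primary analysis after database lock, "when all subjects have completed their 30-day follow-up visit".

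**The concern.** A definition that needs two consecutive misses suits a study with several follow-up visits. This study has one. A subject who attends discharge and then cannot be reached is the ordinary case of loss, and that subject does not meet the definition.

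What is at stake is the account of who was observed to day 30. This is a descriptive safety study, and for a subject with nothing found at discharge the 30-day contact is the only scheduled chance to learn of a later complication. Some descriptive endpoints in Section 4.2 depend on status at that time; nerve injury, for example, is graded by whether it persists beyond 30 days. A disposition table with zero lost to follow-up would tell the reader that ascertainment was complete when the definition could not have produced any other figure.

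**Working it through.** No figure in the plan needs reproducing. The check is a count of scheduled time points against the number that the definition requires.

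**Inputs**
- Consecutive scheduled misses required: 2 (Section 5.5, stated twice).
- Scheduled follow-ups after discharge: 1, at 30 ± 7 days, that is days 23 to 37 (Sections 6.5 and 6.7).
- Later time points: 0, because subjects exit at that visit (Section 5.7).
- Registered subjects: 35 (Section 5.6).

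**Could anything else supply a second time point?**
- *Telephone contact followed by a site visit.* Section 6.5 treats the two as one follow-up: "this site visit is regarded as the 30-day follow-up".
- *Unscheduled visits.* By name and by the Section 6.7 footnote these are optional and follow site standard of care. They are not scheduled, and not having one is no deviation.
- *The discharge assessment.* Section 6.4 treats discharge separately from the 30-day follow-up in Section 6.5. Telephone calls over a follow-up window and then a letter do not fit a subject still in hospital. Even if discharge counted, a subject who was assessed at discharge and then disappeared would have missed only one time point.

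**Result.** Available 1 < required 2, so the condition cannot be met by any subject who vanishes after discharge. Keyed to the 30-day contact alone, required 1 = available 1, and the category works.

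**Scale**
- Each unreachable subject is 1/35 = 2.9% of those registered.
- The documents give no expected loss rate. Assuming 5% to 10%, the expected number with unknown 30-day status is 0.05 × 35 = 1.75 to 0.10 × 35 = 3.5.
- The probability of at least one is 1 − 0.95^35 = 0.834 to 1 − 0.90^35 = 0.975.
- The reported number lost would be 0 throughout that range. The contradiction itself does not depend on the assumed rate.

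**Reach into the primary endpoint.** Section 4.1 counts complications found by scheduled ultrasound at discharge or 30 days in subjects without symptomatic or visible complications. Every subject is scanned at discharge. Under Sections 6.5 and 6.7 the 30-day scan follows only if the discharge scan showed something. Two cases follow:
- Clean discharge scan, then unreachable: a telephone call was due, and a call cannot produce a scheduled-ultrasound finding. A complication that the call brought to light would generally be symptomatic or visible, and so outside the primary analysis.
- Asymptomatic finding at discharge, then unreachable: the subject already counts. What is lost is resolution, later major or minor status, or a new finding on the repeat scan.

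The loss therefore falls mainly on the descriptive 30-day endpoints.

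**The case against.** The strongest reply is that only a label is affected. The list of discontinuation reasons in Section 5.5 is expressly open, so a site can report another reason. A missed 30-day contact is still a missed visit, and because Section 6.5 makes the assessment mandatory it is also a deviation, to be reported under Section 10.6. The calls and the letter are required at each contact time point whether or not the label applies. All of this stands. It rules out saying that such a subject has no place in the records; the point is that the category the plan defines for this situation cannot be used.

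A reader might also infer that unreachable subjects would be counted as free of events in the 30-day denominators. The documents do not support that. Section 8.1 on the analysis population has no text in the public copy, and Section 8.8 refers to a statistical analysis plan with its own amendments. The handling may be set out there.

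Nor does the definition alone create the difficulty in Section 8.4. Read literally, a death or a withdrawal would also leave that condition unmet, so correcting Section 5.5 would not be enough.

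Finally, the study has no hypothesis test (Section 8.6) and no success criterion (Section 8.7), so no decision rule moves. That limits the weight of the point but does not make the definition usable.

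**Conclusion.** The point holds as an internal contradiction. Section 5.5 requires two consecutive scheduled misses and the schedule in Sections 5.7, 6.5 and 6.7 allows one. The lost-to-follow-up count is fixed at zero, and 30-day safety follow-up would look more complete than it may be.

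The size is modest. At 2.9% of registered subjects each, and on an assumed 5% to 10% loss, roughly two to four subjects would have unknown 30-day status without being shown as lost. The consequence is for disposition and the descriptive 30-day endpoints. The primary endpoint is little affected, and no sample size or error rate changes. The conclusion rests on not counting discharge as a follow-up time point, which is how Sections 6.4 and 6.5 read. It makes no claim about how the analysis handles these subjects. The correction is worth making because the rule is wrong as written and costs almost nothing to put right.

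**What to change.** 1. In Section 5.5, define lost to follow-up as no 30-day contact after the two documented calls and the letter already required. State a time allowed for a reply. The letter goes out only after calls made within the window, so a cut-off at day 37 would leave little or no time for an answer.
2. In Section 8.4, let the analysis proceed once every subject has completed 30 days, withdrawn, died or been declared lost.
3. Beside the 30-day descriptive endpoints, report the number with unknown 30-day status. Keep any subject with a complication already observed in both numerator and denominator. Restricting the denominator to known 30-day status could remove a real event: if the only subject with a complication at discharge were then lost, 1/35 = 2.9% would become 0/34 = 0%.

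The cost is wording only. No visit or procedure is added, and the disposition table may show a few lost subjects instead of none.

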5.6 Number of Subjects

A total of 35 subjects will be registered in the clinical study. Of these,

- 8 subjects will be treated with two Perclose SMC for a single access site closure > 8F.
- 12 subjects will have 3 or 4 access sites in a single vein.

5.7 Total Expected Duration of the Clinical Study

The expected duration of registration is 3 months. The expected duration of each subject's participation is 1 month, including the scheduled visits and data collection for this clinical study. Subjects will exit the trial at the end of their 1-month follow-up visit. Therefore, the total duration of the clinical investigation is expected to last 4 months, consisting of approximately 3 months of registration plus 1 month of follow-up.

6.0 TREATMENT AND EVALUATION OF ENDPOINTS

6.1 Baseline/Pre-procedure

All baseline/pre-procedure clinical, laboratory, and imaging assessments should be done per the site standard practice. Demographics and risk factors are listed below to be entered in the eCRF.

6.1.1 Baseline/Pre-procedure Assessment

Demographics

- Gender at Birth
- Birthdate
- Ethnicity
- Race

Risk Factors

- Height
- Weight
- Body Mass Index
- Hypertension
- Dyslipidemia
- Diabetes
- Coronary Artery Disease
- Chronic Kidney Disease
- Congestive Heart Failure
 - Systolic
 - Diastolic
 - Combined
- Cerebrovascular Accident

- Type of Arrhythmia
 - Paroxysmal Atrial Fibrillation (AF)
 - Persistent AF
 - o Atrial Flutter

6.1.2 Chronic concomitant Medications

Chronic concomitant anticoagulants and antiplatelet medications should be recorded. These concomitant medications may be stopped several days before the procedure, and in such a case stop and restart date should be recorded in the eCRF. If the subject stops medications one day prior and resume post-procedure, it is still recorded.

Oral Anticoagulation

- Warfarin
- Apixaban
- Rivaroxaban
- Dabigatran
- Edoxaban
- Other (specify)

Oral Antiplatelet

- Aspirin
- Clopidogrel
- Prasugrel
- Ticagrelor
- Other (specify)

6.2 Ablation Procedure including Access Site Closure with Perclose SMC

6.2.1 Procedural Medication

Procedural medications, including anticoagulants, should be administered per site standard. The type of anticoagulant should be recorded in the eCRF.

Procedural Anticoagulation

- Heparin
- Bivalirudin
- Other (specify)

6.2.2 Vein access and Pre-close

Investigators should use site standard practice to obtain vein access sites for catheter insertion. Locations of the access sites (left or right femoral vein), sheath sizes must be recorded in the eCRF.

If the pre-close technique is used for the Perclose SMC, the subject is considered to be registered in this study at the point the first Perclose SMC is inserted into the body (proximal tip of the Perclose SMC crosses the distal end of the sheath).

In the case that an access site cannot be successfully obtained, a subject should be treated per the site standard practice and not be registered in this study (even though sutures are already placed using the pre-closure technique).

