3.1 Clinical Investigation Procedures and Follow-up Schedule

The study flowchart is shown in **Figure 3-1**. A subject who is planned to have an ablation procedure and satisfies the eligibility criteria will be registered in this trial. Written informed consent must be obtained prior to the registration.

[figure not shown]
The ablation procedure and access site closure should be done per the site's standard practice. If the pre-close technique is used, the subject is considered to be registered in this study at the insertion of the 1st Perclose SMC into the body (in the case that the ablation procedure is not performed after pre-close by the Perclose, then the subject will be de-registered). If only the post-close technique is used, the subject is considered to be registered in this study at the insertion of the 1st Perclose SMC into the body after the ablation procedure.

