5.0 SUBJECT SELECTION AND WITHDRAWAL

5.1 Subject Population

This clinical study will register subjects of all genders who are planned to have elective ablation procedures requiring multiple vein access sites in a single femoral vein. Subjects must meet all eligibility criteria and provide written informed consent prior to registration in this study. Although complications are collected from all registered subjects, primary endpoint analysis is performed only in subjects with asymptomatic/non-visible complications, as the objective of this study is to understand asymptomatic/non-visible complications only observed by DUS.

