7.3 Adverse Event and Device Deficiency/Device Malfunction Reporting

7.3.1 Adverse Event (AE) Reporting

In this study, all vascular complications (regardless of the seriousness), all serious adverse events, procedure-related adverse events, and adverse device effects related to Perclose SMC must be reported.

Safety surveillance and reporting starts when the first Perclose SMC enters the subject's vasculature and will continue until a 30-day follow-up visit has been performed, unless the subject is deceased, or the subject withdraws from the clinical study. Adverse events will not be collected on de-registered subjects (unless specifically required by the CIP or requested by the regulatory authority). Safety surveillance and reporting will continue until sites perform the last follow-up visit, the subject is deceased, the subject concludes participation in the clinical investigation, or the subject withdraws from the clinical investigation. Sites will collect all adverse event data, including deaths and device deficiency data (if applicable), throughout the period defined above and will report these events to the Sponsor on a CRF. Sites should update additional information regarding an adverse event on the appropriate CRF.

Unchanged, chronic, non-worsening, or pre-existing conditions are not AEs and should not be reported.

The investigator must report all SAEs to the Sponsor as soon as possible but no later than outlined below.

Clinical Site	Reporting timelines
All Sites	SAEs must be reported to the Sponsor no later than 3 calendar days
	from the day the site personnel became aware of the event or as per the investigative site's local requirements, if the requirement is more stringent than those outlined above.

The Sponsor will provide an offline form to allow the investigator to report SAEs in the event the entry cannot be made in the Electronic Data Capture (EDC). This does not replace the EDC reporting system. Sites should still enter all information in the EDC system as soon as feasible.

The date the site staff became aware the event met the criteria of an SAE must be recorded in the source document. The Investigator will further report the SAE to the local IRB according to the institution's IRB reporting requirements.

Adverse Device Effect (ADE)

An adverse event related to the use of an investigational medical device.

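### Adverse events are not collected in de-registered subjects who have already received the closure device, and the label in section 6.2.2 leaves it unclear whether failed-access subjects fall under the same rule

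*Combined protocol and SAP*

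**What the plan says.** **Registration.** Section 6.2.2 states that with pre-close "the subject is considered to be registered in this study at the point the first Perclose SMC is inserted into the body". Section 5.4 agrees and names no exception: "If pre-close technique is used, the subject is considered to be registered even before the ablation procedure".

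**Leaving the study after insertion.** There are two provisions. Section 3.1 says "in the case that the ablation procedure is not performed after pre-close by the Perclose, then the subject will be de-registered". The last paragraph of section 6.2.2 deals with an access site that cannot be obtained. The subject is then treated by site standard and should "not be registered in this study (even though sutures are already placed using the pre-closure technique".

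**Adverse events.** Section 7.3.1 opens the collection window at exposure: "Safety surveillance and reporting starts when the first Perclose SMC enters the subject's vasculature". It then closes it for one group: "Adverse events will not be collected on de-registered subjects (unless specifically required by the CIP or requested by the regulatory authority". It also lists the general end points of collection: "Safety surveillance and reporting will continue until sites perform the last follow-up visit, the subject is deceased, the subject concludes participation", or withdraws.

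**Other data.** Section 5.1 describes the scope of complication data in the words "Although complications are collected from all registered subjects". The discharge ultrasound (6.4), the 30-day assessment (6.5) and the eCRF (11.4) are likewise tied to registered subjects.

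**The concern.** This is a device-safety study, and sections 7.0 and 7.3.1 make every vascular complication reportable whatever its seriousness. A pre-close subject is exposed to the device before it is known whether access and ablation will be completed. If safety collection then depends on completing the procedure, some exposed subjects leave the safety record because of something that happened after exposure. Nothing in the documents shows that their complications would be fewer, more frequent or of another kind.

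What is at stake is the completeness of the descriptive complication and adverse-event results (4.2, 7.0). There is also a consistency question for the failed-access group. One site could report a hematoma in such a subject because surveillance began at device entry. Another could leave it out because the subject was never registered. Each could point to the text.

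**Working it through.** There is no stated figure to reproduce: no hypothesis test is planned (8.6), and the visible text gives no rate of de-registration. The check is a side-by-side reading.

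**Step 1. Follow each type of pre-close subject through the text.**

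| Subject | Status at insertion (5.4, 6.2.2) | Later status | Does the 7.3.1 exclusion apply? |
|---|---|---|---|
| A. Ablation not performed | Registered | De-registered (3.1) | Yes, expressly |
| B. Access site fails, sutures placed, ablation not performed | Registered | Not registered (6.2.2); also fits 3.1 | Probably, through 3.1 |
| C. Access site fails, sutures placed, ablation goes ahead | Registered | Not registered (6.2.2); 3.1 does not apply | Not stated |

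In A the rule is clear and internally consistent. The objection there is to what it omits. In C the wording is unclear, because section 7.3.1 names only de-registered subjects. B depends on which section a site consults.

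**Step 2. Test the two exceptions in section 7.3.1.** The first needs a specific requirement in the protocol. Section 7.0 requires vascular complications to be recorded but does not mention de-registered subjects. If that general rule were enough, the exclusion would have no effect on vascular complications at all. No other visible section specifically requires adverse-event collection after de-registration. The second exception, a request by the regulatory authority, is not something a site can plan on.

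**Step 3. Look for other routes.**
- Unanticipated serious adverse device effects are reported under 7.3.2. By the definition in 7.2.1, these must be unforeseen in nature, severity or incidence.
- Device deficiencies and malfunctions, including those in de-registered subjects, are reported under 7.3.3, with onward reporting by the sponsor under 7.3.4.
- Sections 5.5 and 11.0 record why a subject discontinued, not what complications the subject had. Neither says that it covers subjects labelled as not registered.

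**Step 4. What is left.** A hematoma or deep vein thrombosis of expected nature and severity, with no deficiency of the device, has no visible route in A. In C its route is ambiguous. Both events are among the complications that section 4.2 sets out to describe.

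**Step 5. Consent.** Section 5.3.1 requires written consent before the procedure, so all three types of subject have consented before exposure.

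**The case against.** The strongest case for the plan is that these subjects lie outside its question. The objective is multiple access site closure in a single vein, assessed by scheduled ultrasound (2.1, 3.0), and someone without completed access or ablation need not represent that setting. The devices are market-released (2.2.1), each site is closed as in single-site closure (2.2.3), and the study-specific procedure is limited to ultrasound (5.2.1). Section 7.1.3 defines a deficiency broadly, including inadequate safety or performance and use error. There are only two sites, and their training covers the protocol. Much of this stands: it justifies keeping these subjects out of the primary analysis, and it makes the gap narrow. It does not supply a route for an anticipated complication without a deficiency.

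A reader might also infer more than the documents support:

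- *That section 6.2.2 flatly contradicts itself.* The parenthesis about sutures acknowledges that a device has already gone in, so the paragraph reads most naturally as an exception. What is wrong is the label.
- *That section 7.3.1 contradicts its own end of surveillance.* One of the listed end points is that the subject concludes participation, and de-registration is naturally read as that.
- *That the reported complication rate would shift by a stated amount.* Any such figure would need an assumed number of omitted subjects and events. It would also pool subjects who had the required discharge ultrasound with others who need not have had it, an analysis that nobody proposes.
- *That exposed subjects have no safety route at all.* Sections 7.3.2 to 7.3.4 still apply as described.

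**Conclusion.** The point holds and should be fixed. Sections 3.1 and 7.3.1 together leave anticipated vascular complications uncollected in consented subjects who have received the device. Section 6.2.2 leaves it open whether the same exclusion covers failed-access subjects with sutures placed. The first is a gap in a consistent rule; the second is an inconsistent label.

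Size and direction are unknown, because the documents give neither a rate of nor reasons for de-registration. No pooled rate should be quoted. The effect is confined to the descriptive complication and adverse-event results. The conclusion rests on the visible text only: the wording of section 8.1 and the case report forms cannot be seen in this copy, and either could say how these subjects are handled.

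**What to change.** 1. Reconcile sections 3.1, 5.4, 6.2.2 and 7.3.1, together with 5.1 and 11.4, so that one label and one rule cover pre-close subjects who do not complete access or ablation.
2. Replace the exclusion in 7.3.1 with a requirement to record vascular complications, serious adverse events and adverse device effects from first Perclose insertion in every consented, device-exposed subject, including those de-registered.
3. State when surveillance ends for de-registered subjects, for example at the same 30-day contact by telephone. No extra ultrasound is needed.
4. In the report, give the number of such subjects, the reason for each and their events in a separate listing. Leave the primary ultrasound endpoint, the device-success analysis and the target of 35 as they are.

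The cost is a protocol amendment with IRB approval, a change in eCRF scope, and a few additional records and telephone contacts. The safety listing may look slightly less favourable. No new consent step is needed, because consent already precedes the procedure.
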